9.4.2. Follow-up reminder process

The HCP database will be routinely updated with responders and, will be cross-checked with any correspondence that had an invalid address, bounced back or had incorrect contact details.

If no response was received, additional mailings will be sent, with up to a total of three invitations within the 60-90 days data collection period to participate in the web-based survey.

9.5. Study Size

At the time of protocol writing, a total of HCPs (distribution list shared with Saudi Food and Drug Authority [SFDA]) are expected to initiate or manage patients on Vfend®. All HCPs who were targeted to receive the RM tools (per Pfizer Inc.'s Distribution List.) within the 12 months preceding the initiation of the survey will be invited to participate in the survey. Given this relatively small pool of HCPs, an empirical sample size of 10 HCPs is proposed. Data will be collected until 10 completed surveys are obtained or up to a data collection period of 60 to 90 days as a maximum. It is important to note that the final survey sample size will depend on HCPs' willingness to participate in the survey.

An a priori threshold of 80% correct responses per risk question will be used to define the success of the program. However, this criterion will not be used for formal statistical testing. The selection of this threshold for success was regarded as being subjective and not based on prior knowledge, experience, or established scientific criteria.

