9.7. Data analysis

Detailed methodology for summary and statistical analyses of data collected in this study will be documented in a Statistical Analysis Plan (SAP), which will be dated, filed and maintained by the Sponsor. The SAP may modify the plans outlined in the protocol; any major modifications of primary endpoint definitions or their analyses would be reflected in a protocol amendment.

Data collected from the survey will be reported as descriptive statistics. Frequency distributions with 95% CIs will be calculated for HCPs' responses to all questions that address the survey objectives.

Endpoints

- 1. Assess HCPs' awareness of the RM tools (ie, HCP Checklist, HCP Q&A Brochure and Patient Alert Card) by estimating the proportion of targeted HCPs who acknowledge receiving the tools.
- 2. Assess HCPs' utilization of the RM tools (ie, HCP Checklist, HCP Q&A Brochure and Patient Alert Card) by estimating the proportion of targeted HCPs who acknowledge reading and utilizing the tools.
- 3. Assess HCPs' knowledge of the risks of phototoxicity, SCC of the skin and hepatic toxicity with voriconazole by estimating the proportion of targeted HCPs with correct responses to risk knowledge questions.
- 4. Assess whether HCPs' self reported behaviour/practices with respect to minimizing the risks of phototoxicity, SCC of the skin and hepatic toxicity are in accordance with the voriconazole SPC.1 This will be evaluated by estimating the proportion of targeted HCPs whose responses to the practice related questions are consistent with the SPC's1 prescribing information.

In the survey, the proportion of correct or desirable responses across all questions related to the evaluation of the objectives of the surveys will be considered to assess the success.

The questions considered as complementary will not be included in the assessment of success. The details of the assessment of the success for each survey and each objective are described in the "Assessment of Success" document.

Redacted

As described in the Guideline on Good Pharmacovigilance Practices (GVP) Version 3.1 30 January 2023 - Drug Sector, Redacted 1 the percentage of participants responding correctly to the knowledge questions will be analysed and discussed. The minimum acceptable threshold of knowledge will be defined at 80% correct response rate per risk questions.

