Knowledge about the RM tools	Q7. According to the SPC/PI, the known risks for VFEND (voriconazole) are as follows: (Please select only one response for each of the risks listed in the table below.) Q8. Please select only one response for each statement about VFEND	Yes	Question completed correctly (6 points) Question completed correctly (5 points)	An HCP is considered successful for Knowledge when he/she provides at least 9 out of 11 (~80%) correct/desirable responses. Success for
Self-declared behavior/ Practice	(voriconazole) below: Q18. Which precautionary measures do you communicate to your patients for whom you	Yes	Question completed desirably (6 points)	Knowledge: if ≥80% of HCPs are successful An HCP is considered successful for awareness when he/she provides
	prescribe VFEND (voriconazole)? Please check all that apply. 18.a Do you, or another member of your healthcare team (e.g., nurse, pharmacist or other) perform each of these activities when initiating treatment with VFEND (voriconazole)? (Please check one response for each activity below).	Yes	Question completed desirably (6 points)	desirable responses to all sub-questions. Success for self-reported practices if ≥80% of HCPs are successful
	Q19. How frequently do you perform Liver Function Tests (specifically AST, ALT)?	Yes	Question completed desirably (Answer 1 is desirable)	

Q20. If there are no changes in Liver Function Tests (LFTs) after one month of initiation of VFEND (voriconazole), how often do you monitor liver function during VFEND treatment maintenance?	Yes	Question completed desirably (Answer 2 is desirable)	
Q21. How often do you perform a dermatologic evaluation when VFEND (voriconazole) is continuously used despite the occurrence of phototoxicity related lesions?	Yes	Question completed desirably (Answer 4 is desirable)	
Q22. For which of below condition(s) would you discontinue VFEND (voriconazole) in a patient? (Select the one best response).	Yes	Question completed desirably (Answer 4 is desirable)	

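### For the Knowledge objective, Section 9.5 and Section 9.7 judge success per risk question while Annex 1.5 judges it by a 9-of-11 score per HCP, and the same answers can pass one rule and fail the other

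*Protocol*

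**What the plan says.** Section 9.5 (Study Size) sets the decision rule: "An a priori threshold of 80% correct responses per risk question will be used to define the success of the program". It adds that the criterion is subjective and will not be formally tested. Section 9.7 (Data analysis) repeats it: "The minimum acceptable threshold of knowledge will be defined at 80% correct response rate per risk questions". Section 9.9.2 and the abstract in Annex 1.1 say the same.

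Section 9.7 also says that "the proportion of correct or desirable responses across all questions related to the evaluation of the objectives of the surveys will be considered" in assessing success, and refers to the annex for the detail: "The details of the assessment of the success for each survey and each objective are described in the" separate Assessment of Success document.

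That document, Annex 1.5, has no per-question threshold. It first scores each respondent: "An HCP is considered successful for Knowledge when he/she provides at least 9 out of 11 (~80%) correct/desirable responses". It then sets success for "Knowledge: if ≥80% of HCPs are successful". For self-reported practice it asks for "desirable responses to all sub-questions. Success for self-reported practices if ≥80% of HCPs are successful".

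**The concern.** The body counts HCPs item by item. The annex counts items HCP by HCP, lets any two be missed, and then counts HCPs. These are different statistics, and nothing in the protocol says which gives the Knowledge verdict.

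There is no formal test, so the 80% threshold is the only decision rule in a report that goes to the SFDA. With two rules written down, the verdict could be chosen after the answers are known. The annex rule can also attach a success label when one key risk message has not reached anyone. Section 9.9.2 itself expects knowledge to differ by key risk message.

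**Working it through.** **Inputs**
- Respondents: 10 HCPs (Section 9.5).
- Knowledge points: Q7 has 6 rows and Q8 has 5 statements, 11 in all (Annexes 1.2 and 1.5).
- Items by risk, from Annex 1.2: phototoxicity 2 (one Q7 row, one Q8 statement); SCC 2, or 3 if the Q8 statement on treatment beyond 6 months is counted as SCC; hepatic toxicity 3 (one Q7 row, two Q8 statements).
- The other three Q7 rows (intestinal perforation, asthma, cardiomyopathy) are outside the three risks and are read here as decoys. That leaves 11 − 3 = 8 risk items.

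**The plan's own figure.** 0.80 × 11 = 8.8, rounded up to 9, and 9/11 = 81.8%. The annex's approximate 80% is reproduced. At HCP level, 80% of 10 is 8.

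**Case A: annex passes, body fails.** All 10 HCPs miss both phototoxicity items and get the rest right.
- Annex: each scores 11 − 2 = 9, so 10/10 = 100% are successful and Knowledge is a success.
- Body: 0/10 = 0% on each of the two phototoxicity items, so the threshold is missed.

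**Case B: annex fails, body passes.** Each of the 11 items is missed by exactly one HCP, and the 11 errors fall on three HCPs as 3, 4 and 4.
- Body: every item is 9/10 = 90% correct, so the threshold is met throughout.
- Annex: those three score 8, 7 and 7, all below 9. Only 7/10 = 70% are successful, so Knowledge fails.

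Both cases are counting only and need no probability model.

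**How hard each rule is to meet.** For illustration, assume independent items with a common true probability p of a correct answer.
- Annex: h = P(Bin(11, p) ≥ 9), then P(Bin(10, h) ≥ 8).
- Per item: g = P(Bin(10, p) ≥ 8), then g^8 for all eight risk items.

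| p | h | Annex rule met | g | All 8 risk items met |
|---|---|---|---|---|
| 0.80 | 0.617 | 0.197 | 0.678 | 0.045 |
| 0.90 | 0.910 | 0.947 | 0.930 | 0.56 |

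On these assumptions the per-item rule is the harder one.

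**Practice, for context.** Q18 (6) + Q18a (6) + Q19 to Q22 (4) = 16 points when the Patient Alert Card row of Q18a is shown. It appears only if Q11 or Q12 is answered yes. Under independence, for 80% of HCPs to get all 16, each point needs 0.80^(1/16) = 0.986 desirable.

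**The case against.** The strongest defence is that Annex 1.5 simply puts the body's 80% into operation. Section 9.7 refers to it for detail, Sections 9.7 and 9.9.2 use the plural for risk questions, and the annex labels 9 of 11 as about 80%. This does not hold: Section 9.5 uses the singular, Section 9.7 restates the threshold after pointing to the annex, and Cases A and B show that the annex can reverse the body's verdict.

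Other points on that side do stand.
- Section 9.7 requires the number and percentage correct for each question or item, and 95% CIs for responses. A 0% phototoxicity result would be visible in the report; only the success label could mislead.
- A reader might count the sentence about all questions in Section 9.7 as a third rival rule. It gives no threshold and leads into the reference to the annex, so it is better read as an introduction that needs aligning.
- A reader might think the annex's practice rule also contradicts the body. It does not: the body's threshold concerns knowledge of the risks, Section 9.4 assigns that to Q7 and Q8, and no per-item practice threshold is set. The practice rule is far stricter than an 80% standard, but that is a design choice.
- A reader might take the low 0.197 at a true 80% as showing the annex to be the stricter rule for Knowledge. On the same assumptions the per-item figure is 0.045.

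**Conclusion.** The protocol states two conflicting success rules for the Knowledge objective, and identical answers from 10 HCPs can give opposite verdicts: 100% of HCPs successful with 0% correct on phototoxicity, or 70% successful with every item at 90%. This should be corrected before data are seen.

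Two wider readings are not supported. Annex 1.5 gives verdicts objective by objective and nowhere combines them, so Case A makes Knowledge a success, not the whole programme. Nor can every risk be missed entirely and still pass: phototoxicity can, and SCC can if counted as two items, but missing all three hepatic items gives 8/11 and fails.

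The conclusion takes a risk question to be each row or statement, which matches the item-level reporting in Section 9.7. If Q7 and Q8 were each pooled instead, Case A would give 5/6 = 83% and 4/5 = 80% and no longer conflict with the annex. Case B would still conflict, at 90% on each. The probabilities in the table assume independent items with equal difficulty; the same HCP answers all of them, so those figures are illustrative.

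**What to change.** Amend the Knowledge entry in Annex 1.5 so that the verdict follows the body: at least 80% of HCPs correct on each phototoxicity, SCC and hepatic item in Q7 and Q8. State that a risk question means the individual row or statement. Report the three other Q7 rows and the 9-of-11 score descriptively, so that they cannot offset a missed risk item. Reword the sentence about all questions in Section 9.7 to agree.

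This changes wording only; the questionnaire and data collection stay as they are. The price is that with 10 HCPs the per-item rule is harder to meet (about 0.56 against 0.95 at a true 90% correct, under independence), so one weak item may fail by chance. Each item result should therefore stand beside its 95% CI in the report. The practice rule need not change on this ground, though the sponsor may wish to confirm that a standard needing about 98.6% per point is intended.

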9.6. Data management

All data collected during the survey will be held confidentially by the vendor. The data collection tool (DCT) [Decipher] used for data collection encrypts all identifiable information, and respondents' IDs are stored separately from the survey responses.

Skip logic for certain questions as well as the ability to mark only one response or multiple responses are part of the programming for the survey administration, which minimises the occurrence of data entry errors. There will be no queries to respondents for this project.

9.6.1. Data collection tools (DCTs)

All surveys are programmed internally using Redacted Decipher system, a secure online data collection software. Redacted guarantees senior-level programming support on all research engagements, with programmers who have been trained using a stringent quality control process to ensure that the surveys are programmed error-free. Redacted utilizes a rigorous quality assurance process which includes the following:

- Programmer and researcher manual testing: Manual testing process which includes several members of the research and programming team (Operations) testing each survey path thoroughly to ensure accuracy in both the text and all survey logic (skip and jump patterns). Each survey is tested on stimulator associated with the web browsers.
- Random Data Generation (RDG) and Data Check Edits (DCE): Once testing is completed by both the operations and research teams, a member of the operations team runs a set of randomly generated data ("dummy" data) to fill all possible paths and quotas, then writes a programmatic check designed to test the validity of the survey. Each question is tested for the correct number and coding of responses, that respondents answering the questions meet the base criteria as well as duplicate any calculated or algorithmic variables and compared for accuracy. An independent member of the operations team then writes the DCE. The data is also run through the DCE one again with soft launch data, full field data (data from the day after full fielding has begun) and the final data set.

As used in this protocol, the term DCTs should be understood to refer to either a paper form or an electronic data record or both, depending on the data collection method used in this study. A completed DCT is required for each included participant. The completed original DCTs are the sole property of Pfizer and should not be made available in any form to third parties, except for authorized representatives of Pfizer or appropriate regulatory authorities, without written permission from Pfizer. Redacted shall ensure that the DCTs are securely stored in Decipher in encrypted electronic form and will be password protected to prevent access by unauthorized third parties.

has ultimate responsibility for the collection and reporting of all data entered on the DCTs as required and ensuring that they are accurate, authentic/original, attributable, complete, consistent, legible, timely (contemporaneous), enduring, and available when required. The DCT serves as the source document.

9.6.2. Record retention

To enable evaluations and/or inspections/audits from regulatory authorities or Pfizer, agrees to keep all study-related records. The records should be retained by to local regulations or for the period specified by the sponsor, whichever is longer. Redacted must ensure that the records continue to be stored securely for so long as they are retained.

If **Recorded** becomes unable for any reason to continue to retain study records for the required period, Pfizer should be prospectively notified. The study records must be transferred to a designee acceptable to Pfizer.

Study records must be kept for a minimum of 15 years after completion or discontinuation of the study, unless redacted and Pfizer have expressly agreed to a different period of retention via a separate written agreement. Record must be retained for longer than 15 years if required by applicable local regulations. redacted must obtain Pfizer's written permission before disposing of any records, even if retention requirements have been met.

9.7. Data analysis

Detailed methodology for summary and statistical analyses of data collected in this study will be documented in a Statistical Analysis Plan (SAP), which will be dated, filed and maintained by the Sponsor. The SAP may modify the plans outlined in the protocol; any major modifications of primary endpoint definitions or their analyses would be reflected in a protocol amendment.

Data collected from the survey will be reported as descriptive statistics. Frequency distributions with 95% CIs will be calculated for HCPs' responses to all questions that address the survey objectives.

Endpoints

- 1. Assess HCPs' awareness of the RM tools (ie, HCP Checklist, HCP Q&A Brochure and Patient Alert Card) by estimating the proportion of targeted HCPs who acknowledge receiving the tools.
- 2. Assess HCPs' utilization of the RM tools (ie, HCP Checklist, HCP Q&A Brochure and Patient Alert Card) by estimating the proportion of targeted HCPs who acknowledge reading and utilizing the tools.
- 3. Assess HCPs' knowledge of the risks of phototoxicity, SCC of the skin and hepatic toxicity with voriconazole by estimating the proportion of targeted HCPs with correct responses to risk knowledge questions.
- 4. Assess whether HCPs' self reported behaviour/practices with respect to minimizing the risks of phototoxicity, SCC of the skin and hepatic toxicity are in accordance with the voriconazole SPC.1 This will be evaluated by estimating the proportion of targeted HCPs whose responses to the practice related questions are consistent with the SPC's1 prescribing information.

In the survey, the proportion of correct or desirable responses across all questions related to the evaluation of the objectives of the surveys will be considered to assess the success.

The questions considered as complementary will not be included in the assessment of success. The details of the assessment of the success for each survey and each objective are described in the "Assessment of Success" document.

Redacted

As described in the Guideline on Good Pharmacovigilance Practices (GVP) Version 3.1 30 January 2023 - Drug Sector, Redacted 1 the percentage of participants responding correctly to the knowledge questions will be analysed and discussed. The minimum acceptable threshold of knowledge will be defined at 80% correct response rate per risk questions.

The distribution of the responses to questions assessing all study objectives will be presented in the study report. It is to be noted that the selection of this threshold for success is subjective and not based on a priori knowledge, experience, or established scientific criteria in the education or risk communication or evaluation literature. Therefore, the results will be contextualized within the context of other available information.

The following will be reported as part of the analysis:

• Survey administration

- The number of HCPs by select medical specialty (ie, infectious disease physicians, pharmacists, as applicable).
- The number of survey invitations issued by strata (ie, by speciality).
- The number of survey invitations returned due to incorrect E-mail address of HCPs invited to participate in the survey.

• Demographic characteristics of participants

- Distribution of participants by region.
- Distribution by medical specialty.
- Distribution of participants by years in medical practice.
- Distribution of participants by number of patients treated with voriconazole in the past 12 months.
- HCP responses to questions pertaining to the survey objectives:

1. Awareness of the RM tools.

• The number and percentage of HCPs who acknowledged receiving each of the tools.

2. Utilization of the RM tools

- The number and percentage of HCPs indicating which tools they utilized when treating patients with voriconazole.
- The number and percentage of HCPs indicating they read tools.

3. HCP's knowledge/understanding of the risks

• The number and percentage of HCPs who correctly responded to each question/item about the risks of phototoxicity, SCC of the skin and hepatic toxicity with voriconazole.

4. HCPs' self-reported practices

• The number and proportion of HCPs whose responses to each behavior/practice related questions are consistent with the SPC¹ prescribing information.

Analysis of participation rate

The following different cases will be distinguished:

- HCPs who do not participate (R): HCPs who do not respond or that explicitly indicate their refusal to participate.
- HCPs with partially answered questionnaires (P): HCPs click on the link provided in the invitation email, and who begin answering the questionnaire but never submit it.
- Failed screening (F): HCPs who will not be eligible for the survey (HCPs who will not meet inclusion criteria and/or who will meet any of the exclusion criteria).
- HCPs with completed questionnaire (C): HCPs who complete the entire questionnaire and submit it.
- Contacted HCPs: HCPs who are contacted by phone or who receive a web link to the online survey via email = C+P+R+F.
- HCPs who agree to participate: HCPs willing to participate in the survey (e.g., by clicking on the link provided in the invitation email) = P+C.
- The HCPs participation in the survey will be examined as follows:

Response rate =
$$\frac{C}{C+P+R}$$

Refusal rate =
$$\frac{R}{C+P+R}$$

The details of analysis will be provided in the SAP.

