All questions must be answered in order to complete the survey. In each survey, response options presented in a list will be presented in random order (where appropriate) to minimise positional bias. Programming will be reviewed by quality control and simulated users (User Acceptance Testing) prior to implementing the survey.

2. Generalization of the survey results to the overall target population

In such surveys, the generalization and external validity of the results is restricted to HCPs who can be reached and are willing (and able) to answer a questionnaire online questionnaire. These HCPs may not be fully representative of the whole target population.

The study report will discuss the results in the light of the limitations described above including variability and uncertainty of the data and methods.

Redacted

Finally, the marketing authorization holder (MAH) acknowledges that an a priori threshold of 80% correct per risk questions will be used to define the success of the program. However as acknowledged by EMA, the selection of this threshold for success is subjective (7 May 2015 PRAC Rapporteur PASS Protocol Assessment Report; Procedure no.: EMEA/H/C/000387/MEA 087.2) and not based on a prior knowledge, experience, or established scientific criteria in the education or risk communication literature. The MAH expects that the knowledge may differ by key risk message, clinical practice, & HCP specialties. Moreover, sample size may not be sufficient to conduct subgroup or stratified analyses.

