Annex 1.5. Assessment of success

Objectives	Questions	Is the question included in the assessment of success? (Yes/No)	Definition of desirably/correctly answered question	Assessment of success
Awareness of the RM tools	Q9. Did you or your hospital receive the VFEND (voriconazole) Healthcare Professional (HCP) Q&A Brochure?	Yes	Question completed desirably (Answer 1 is desirable)	An HCP is considered successful for awareness when he/she
	Q10. Did you or your hospital receive copies of the VFEND (voriconazole) Healthcare Professional (HCP) Checklist?	Yes	Question completed desirably (Answer 1 is desirable)	acknowledges receiving all RM tools Success for awareness: if
	Q11. Did you or your hospital receive copies of the VFEND (voriconazole) Patient Alert Card?	Yes	Question completed desirably (Answer 1 is desirable)	≥80% of HCPs are successful
	Q12. Did you or another staff member obtain the VFEND (voriconazole) RM tools by downloading them from a website?	No	Complementary question	
Reading and Utilizing the tools.	Q9.1 Did you read the VFEND (voriconazole) HCP Q&A Brochure?	Yes	Question completed desirably (Answers 1 & 2 are desirable)	An HCP is considered successful for utilization when
	Q10.1 Did you read the VFEND (voriconazole) Healthcare Professional (HCP) Checklist?	Yes	Question completed desirably (Answers 1 & 2 are desirable)	he/she reports reading all/some of all RM tools and
	Q11.1 Did you read the VFEND (voriconazole) Patient Alert Card?	Yes	Question completed desirably (Answers 1 & 2 are desirable)	always/sometim es using them Success for
	Q14. When treating patients with VFEND (voriconazole) in the past 12 months, how often did you use the VFEND HCP Checklist?	Yes	Question completed desirably (Answers 1 & 2 are desirable)	utilization: if ≥80% of HCPs are successful
	Q15. When treating patients with VFEND (voriconazole) in the past 12 months, how often did you use the HCP Q&A Brochure?	Yes	Question completed desirably (Answers 1 & 2 are desirable)	

	Q16. When treating patients with VFEND (voriconazole) in the past 12 months, how often did you distribute and fill in the Patient Alert Card? Q17. Did you find the VFEND (voriconazole) RM tools to be of use in your clinical practice? Please select only one rank for each RM tool (Q17.1, Q17.2 and Q17.3)	Yes No	Question completed desirably (Answers 1 & 2 are desirable) Complementary question	

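### Programme success is decided by different rules in sections 9.5, 9.7 and Annex 1.5, and the same 10 surveys can meet one rule and fail another

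*Protocol*

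**What the plan says.** Section 8 poses one overall question, whether the additional risk minimisation measures are effective, and splits it into four objectives: awareness, utilisation, knowledge and self-reported practice. Success is then defined in three places.

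- **Risk questions alone.** Section 9.5: "An a priori threshold of 80% correct responses per risk question will be used to define the success of the program". Annex 1.1 repeats this, and section 9.9.2 says again that a "threshold of 80% correct per risk questions will be used to define the success of the program". Section 9.4 points the same way by presenting the knowledge level as the effectiveness of the measures. Section 9.7, however, describes the same 80% figure only as the minimum acceptable level of knowledge.
- **All questions of all objectives.** Section 9.7: "the proportion of correct or desirable responses across all questions related to the evaluation of the objectives of the surveys will be considered" in order to judge success. Only complementary questions are left out, and no cut-off is attached. It then adds: "The details of the assessment of the success for each survey and each objective are described in the 'Assessment of Success' document".
- **Four verdicts counted in HCPs.** Annex 1.5 first classifies each HCP on each objective, then asks whether at least 80% of HCPs succeeded. For practice it reads "Success for self-reported practices if ≥80% of HCPs are successful", and the other three objectives have the same form. Nothing says how the four verdicts bear on the programme.

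The planned size is small ("an empirical sample size of 10 HCPs is proposed"), and section 9.5 rules out formal testing of the threshold.

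**The concern.** A criterion set in advance is useful only if it gives one answer for one data set. Here the deciding objective differs (knowledge alone, or all four), and so does the unit that is counted (the question, the response or the HCP). The final report goes to the regulator. Its authors could call the programme successful because each risk question reached 80%, although most HCPs failed on awareness or practice. They could equally have to call it unsuccessful because of one question, although every objective was met. Which label appears would depend on the section followed, and that choice could be made after the results are known.

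**Working it through.** **Inputs.** 10 completed surveys (section 9.5). Scored items from Annex 1.5: awareness 3 (Q9–Q11); utilisation 6 (Q9.1, Q10.1, Q11.1, Q14–Q16); knowledge 6 + 5 = 11 (Q7, Q8); practice 6 + 6 + 4 = 16 (Q18, Q18a, Q19–Q22). Total 3 + 6 + 11 + 16 = 36 items, so 360 responses. An HCP succeeds on awareness, utilisation and practice only with every item, and on knowledge with at least 9 of 11.

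**The plan's own figure.** 0.80 × 11 = 8.8, rounded up to 9. 9/11 = 81.8% and 8/11 = 72.7%, so the stated 9 of 11 (about 80%) reproduces. At least 80% of 10 HCPs means at least 8.

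**Assumptions.** The per-question rule requires every one of the 11 items to reach 80%, and all 10 HCPs are in every denominator.

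**Data set A.** Each knowledge item 9/10, each awareness and utilisation item 6/10, each practice item 7/10.

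- Per-question rule: every risk question at 90%. Met.
- Annex 1.5: an HCP must have every item, so at most 6/10 succeed on awareness, at most 6/10 on utilisation and at most 7/10 on practice. All three fall short of 8/10.
- Knowledge under Annex 1.5: if one HCP makes all 11 errors, 9/10 HCPs succeed and it passes. If three HCPs make 4, 4 and 3 errors, they score 7, 7 and 8 of 11, only 7/10 succeed, and it fails.
- All-question proportion: (3×6 + 6×6 + 11×9 + 16×7)/360 = (18 + 36 + 99 + 112)/360 = 265/360 = 73.6%. Section 9.7 gives no cut-off to compare this with.

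**Data set B.** One risk item 7/10, everything else 10/10.

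- Per-question rule: one question at 70%. Not met.
- Annex 1.5: three HCPs score 10/11 on knowledge and seven score 11/11, so 10/10 succeed. The other three objectives are also 10/10. All four verdicts pass.
- All-question proportion: (35×10 + 7)/360 = 357/360 = 99.2%.

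**How often the two knowledge rules part.** Illustration only: independent items with one common correct rate p. The per-question rule has probability P(X ≥ 8 | 10, p)^11. The Annex rule has probability P(Y ≥ 8 | 10, h), where h = P(at least 9 of 11 correct | p). Disagreement was simulated.

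| p | Per-question rule met | Annex 1.5 knowledge met | Rules disagree |
|---|---|---|---|
| 0.80 | 0.014 | 0.197 | 0.19 |
| 0.85 | 0.113 | 0.613 | 0.52 |
| 0.90 | 0.449 | 0.947 | 0.51 |
| 0.95 | 0.881 | 0.9996 | 0.12 |

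**The case against.** The best defence is that a coherent reading exists. The risk questions decide for the programme, Annex 1.5 decides for each objective, and the all-questions sentence in 9.7 only says which questions count before handing the scoring to the Annex. Part of this stands: 9.7 does not speak of pooling and sets no cut-off, so it cannot be held to be a third numerical rule. The conflict survives without it. On that reading, data set A gives a successful programme with three of four objectives unmet, and data set B a failed programme with all four met, knowledge included. The documents never state such a hierarchy.

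The protocol also calls the 80% threshold subjective and promises to put results in context. That concerns the value of the threshold, not which rule decides. Nor can the point be left to a SAP, because the contradiction lies within the protocol's own text.

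Four stronger inferences are tempting, and the documents do not support them.

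- *A pooled score could hide a failed objective.* This needs a cut-off that 9.7 does not give. Section 9.7 also commits the report to response distributions and counts under each objective, so a failure would be visible.
- *Four verdicts inflate the chance of a false success.* No section permits a claim based on any one objective, no test is planned, and any such probability would rest on success rates chosen by the reader.
- *Naming no primary endpoint is an error.* Four co-equal descriptive endpoints are legitimate. The word primary appears only in a general clause that "any major modifications of primary endpoint definitions or their analyses would be reflected in a protocol amendment".
- *Programme success must mean all four objectives.* Nothing in the protocol says so.

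**Conclusion.** The point holds as an inconsistency in the pre-set definition of programme success and should be corrected before data collection. Its firmest part is the clash between the per-risk-question rule and Annex 1.5, shown in both directions by data sets A and B. These need no probability model, but they rest on the two stated assumptions. Skip logic matters for utilisation in data set A: if only HCPs who were shown those questions were counted, its denominator would change. The awareness failure does not depend on this, because Q9–Q11 go to every HCP, nor does the practice failure, because Q19–Q22 do too. The disagreement rates of 0.12 to 0.52 are illustrative and depend on independent items with a common rate. Planned reporting by objective limits the harm: the underlying results will be seen, but the success label attached to them is not determined.

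**What to change.** 1. State in 9.7 that Annex 1.5 is the single source of success verdicts, reported objective by objective.
2. In 9.5, 9.9.2 and Annex 1.1, replace the wording that lets the 80% figure define programme success. Make 80% per risk question a descriptive benchmark within the knowledge objective, subordinate to the Annex 1.5 rule (at least 9/11 by at least 80% of HCPs). Otherwise knowledge would keep two criteria.
3. Align with this the knowledge threshold in 9.7 and the sentence in 9.4 that presents knowledge as effectiveness.
4. Reword the all-questions sentence in 9.7 so that it says only which questions count.
5. State that meeting the knowledge criterion, or any one objective, is not reported as success of the programme, and that any overall effectiveness statement names every objective not met.
6. While editing Annex 1.5, correct the practice row, which labels its HCP-level rule as one for awareness.

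The cost is wording only, with no extra data. The downside is that knowledge results alone can no longer support a programme-success claim.

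Requiring all four objectives for an overall success statement is a trade-off for the sponsor and not part of this fix. With independent items answered correctly at a 95% rate and 10 HCPs, the four verdicts have probabilities 0.839, 0.481, 0.9996 and 0.024, and their product is about 0.01.
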